8. We will use the oral morphine conversion table to convert any opiate use to OME for each patient (26).
9. Assess possible complications with each intervention (expected to be low).

Study Population

- All female patients undergoing laparoscopic or robotic hysterectomy at MHH and will be recruited and consented for enrollment by the research team in the preoperative area.

Inclusion Criteria:

- English or Spanish speaking
- American Society of Anesthesiologists (ASA) physical status 1-3,
- Age greater than or equal to 18 years
- Planned laparoscopic or robotic hysterectomy

Exclusion Criteria:

- History of chronic pain requiring preoperative opioids, Known alcoholism disorder
- Congenital coagulopathy,
- Localized soft tissue infection,
- Use of anticoagulants,
- Dementia, inability or refusal to provide consent for the surgery
- Morbid obesity (BMI > 50), due to expected technical difficulty to achieve the block.
- Usual pain management will continue regardless of which arm of the study patients are in and measurements of pain scores, narcotic usage and abdominal numbness will be assessed in the post-operative period.

Study Design and Procedures

The study will be reported according to the CONSORT (Consolidated Standards of Reporting Trials) guidelines (28).

All medications and procedures used in this study (0.25% bupivacaine, dexamethasone, acetaminophen, ibuprofen, QL blocks) are FDA approved and have been determined to be usual care in the coverage analysis.

1- Recruitment and consents:

Patients undergoing laparoscopic or robotic hysterectomy at MHH will be recruited and consented for enrollment and block randomized to one of 2 arms: Local anesthesia and QL block. The regional anesthesia nurse would consent the patients.

Spanish consents are available for Spanish speaking patients.

Patients will not be told if they will be receiving the drug or the control.

Blinding is done by the nurse anesthetist preparing the medication, to assure anesthesiologist and research personnel are blinded to the drug used since each patient will receive the two modalities, with only one containing the active drug.

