Doses of bupivacaine are calculated to stay below the 3mg/kg total dose, and diluted to provide the volume effect of the block (as per usual care).

Block procedures:

The nerve blocks will be placed after the patients are placed under general anesthesia, as is usual.

Skin is prepared twice with application of chlorhexidine 0.5% in ethanol 82%. The block procedure is performed under ultrasound guidance with a curvilinear transducer covered by a sterile transparent plastic sheath.

- The QL block will be administered on both the right and left sides. The transducer is placed transverse immediately cranial to the iliac crest and at the level of the posterior axillary line. The needle is then inserted inplane from the lateral edge of the transducer and advanced through the quadratus lumborum (QL) muscle until the needle tip penetrated the epimysium of the anterior part of the QL muscle. The anesthetic is injected after repeated negative aspiration tests for blood in the fascial interspace between the QL and psoas major (PM) muscles posterior to the transversalis fascia (30-32).

Successful injectate spread is confirmed by turning the transducer 90 degrees into the longitudinal sagittal plane to see separation of the muscle planes in each type of block.

Subjects are monitored with three-lead electrocardiography, pulse oximetry, and noninvasive BP and have two IV lines.

The dermatomal segments of the QL block will be assessed using ice by staff after 1 h in the recovery area, and the rest of the study duration does not involve dermatomal assessment.

The standard ERAS protocol will followed in all patients:

Pre-Op	Intra-Op	Intra-Op	Pointer	Post-Op

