
NON-Diabetics Carbohydrate load
 
Gatorade 8 oz 2 hours before procedure
 
Clear liquids up to 2 hours prior to surgery
 
Tylenol 1gm PO
 
Celecoxib 200mg PO
 
Gabapentin 300-600mg PO
 
Robaxin 750mg PO
 
Scopolamine unless contraindicated (Avoid in males with prostate issues)
 
Reglan-AVOID with bowel obstructions
	
Standard Induction
 
 Reduction/elimination of narcotics beyond induction. 
Decadron 4mg (in non diabetics)
 
Infusions
 
 Propofol (50-150 mcg/kg/min) +/- Dexmedetomidine (200mg/50ccNS) 0.25-0.5mg/kg IV bolus post-induction, then infusion at 0.1-0.3mg/kg/hr *Consideration: Start at 0.4mcg/kg/hr then decrease after 1 hour to 0.2mcg/kg/hr. During closing, decrease to 0.1 mcg/kg/hr Ketamine 10mg/hr or 0.25mg/kg/hr. If not given per infusion, bolus patient with 50mg prior to incision and 1 hour prior to close. Consider 0.125mg/kg injections q30mins IVP if unable to start an infusion. +/- Inhalation agents (<0.5 MAC if used) Acetazolamide (TBD) Max Fentanyl 150 mcg (consider baseline HR and BP) 	
Last hour of case
 
 Terminate Ketamine infusion Zofran 4mg Closing (fascial) Propofol to 1mcg/kg/hr (bolus as needed) Dexmedetomidine Decrease to 0.1 mcg/kg/hr Pressure Support ventilation 60 % FiO2 	
S
 
Goal directed fluid administration ~3-5cc/kg/hr of isotonic fluids (Avoid Normal Saline)
 
Minimal Use of invasive lines, NGTs, drains, foleys, and tubes
 
Glycemic control Blood sugar less than 200 (Glucose checks q hour)
 
Maintenance of core temperature >36 Optimal 37
 
Prevention/Control of nausea and vomiting
 
Lung protective ventilation. Decreased TVs; Increased PEEP (6-8ml/kg IBW PEEP 6-10)
	
 Acetaminophen 650mg by mouth every 4 hours- Celecoxib 200mg by mouth every 12 hours Gabapentin 300mg by mouth every 8 hour Tramadol 50-100mg by mouth every 6 hours as needed for breakthrough pain (pending phone call) If tramadol is ineffective at controlling breakthrough pain, the pain medication will be escalated to scheduled tramadol 100mg every 6 hours with oxycodone 5-10mg every 4 hours as needed for breakthrough pain dependent upon pain score. Can consider Nucynta 
Ondansetron 4mg IV every 6 hours scheduled
 
Promethazine 12.5mg IM every 6 hours as needed for nausea and/or vomiting etc.

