All patients will receive the same post-operative pain medication regimen (this regimen is obtained via consensus from anesthesiologists and surgeons performing minimally invasive hysterectomy).

We will give the patients a Gabapentin, Tramadol prescription (50 mg X15 tablets as the only opiate) in addition to the Ibuprofen and Tylenol (See the ERAS protocol for details).

- Tylenol total 30 tab
- Ibuprofen 600 mg q6hr total 30 tab
- Gabapentin 300 mg total 20 tab
- Tramadol 50 mg total 15 tab

5- Comparison:

The following variables will be recorded to compare the different interventions in the following timeline:

- In PACU: (Registered nurse, performs usual care) data is collected retrospectively by research staff
 - Collect pain score rest and dynamic using the Visual analog scale (VAS)
 - Immediately upon arrival
 - At the time of first opiate use
 - Worst pain score
 - At time of discharge
 - Postoperative nausea and vomiting (PONV) score (worst and at the time of discharge)
 - Time elapsed to first opiate use (in minutes)
 - Cumulative opiate use in OME in PACU
 - patient satisfaction will be measured on a Likert scale (5 points)
 - The incidence of postoperative adverse events such as nausea, vomiting, dizziness, headache, urinary retention, local anesthesia-induced side effects (paresthesia, hearing disturbance, visual disturbance, and dysarthria)
- At 24 hours (+/- 4 hours) telephone call by research assistant blinded to procedure
 - Filled Tramadol (Yes/no)
 - Cumulative opiate use in OME if any (How many Tramadol pills used).
 - QOR-40 (6.3 min validated questionnaire)
 - Dynamic pain score on VAS
 - Patient satisfaction will be measured on a Likert scale (5 points)
- Day 14: (clinic visit, usual care)
 - Filled Tramadol (Yes/no)
 - Cumulative opiate use in OME if any. (Via number of Tramadol pills left)
 - Dynamic pain score on VAS
 - Clinic visit on day 14 (per usual care)
 - Cumulative opiate use in OME if any (Check number of pills of Tramadol left. Versus need for refills).
 - Dynamic pain score on (VAS).
- 6 weeks clinic visit (per usual care)
 - Complications

- Cumulative OME use if any
- Refill on pain meds, yes/no and which medications.

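### The single post-operative analgesic regimen appears in two unreconciled versions, and the 24-hour and day-14 opioid items name only tramadol

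*Combined protocol and SAP*

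**What the plan says.** Two statements make the regimen uniform. Under Block procedures, the ERAS table is introduced with "The standard ERAS protocol will followed in all patients". The text after the table opens with "All patients will receive the same post-operative pain medication regimen".

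The contents differ:

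- **ERAS table, Post-Op column.** The NSAID is "Celecoxib 200mg by mouth every 12 hours"; celecoxib also appears in the Pre-Op column. Tramadol is given as needed. If it fails, the patient moves to scheduled tramadol 100 mg every 6 hours with "oxycodone 5-10mg every 4 hours as needed for breakthrough pain dependent upon pain score", and Nucynta is a further option.
- **Prescription text and list after the table.** The opioid is a "Tramadol prescription (50 mg X15 tablets as the only opiate". This comes "in addition to the Ibuprofen and Tylenol (See the ERAS protocol for details". The list gives ibuprofen 600 mg every 6 hours, 30 tablets, and no celecoxib.

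On measurement, section 5 (Comparison) words the 24-hour item as "Cumulative opiate use in OME if any (How many Tramadol pills used". The first day-14 item derives OME from tramadol pills left; a second day-14 entry sets the pills left against whether a refill was needed.

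**The concern.** The prescription text relies on the ERAS table for its detail, but the table does not contain the NSAID that the text names, and it permits opioids that the text appears to exclude. A clinician cannot tell from the protocol whether one list replaces the other, follows it, or runs alongside it. Read literally, both apply to everyone, and two NSAIDs can overlap. That is a safety matter, and it also loosens the standard background against which the two arms are compared.

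The second issue is measurement. Opioid use at 24 hours and 2 weeks is a named secondary outcome. Under the ERAS rule, the patients who receive oxycodone are those in whom tramadol was not enough. An item that asks only about tramadol is therefore weakest in the patients with most pain. If one arm has more escalation, and so more opioid use, leaving out the non-tramadol part pulls the OME difference towards zero.

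**Working it through.** The plan states no figure on this point to reproduce. The check sets the texts side by side and adds supply arithmetic from the protocol's own doses and tablet counts.

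**1. The two lists**

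| Item | ERAS Post-Op column | Prescription text and list |
|---|---|---|
| NSAID | celecoxib; no ibuprofen anywhere in the table | ibuprofen; no celecoxib |
| First opioid | tramadol 50–100 mg every 6 h as needed | tramadol 50 mg, 15 tablets |
| Other opioids | oxycodone on escalation; Nucynta possible | none; tramadol described as the only one |
| Applies to | all patients | all patients |

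Either list alone gives one NSAID; both together give two. Even if the lists run in sequence, a patient discharged on the day of surgery could have celecoxib from the table and ibuprofen from the prescription within the first 24 hours. The protocol does not say when one list ends and the other begins.

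**2. Tramadol supply**

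- Supply: 15 × 50 mg = 750 mg.
- At 50 mg every 6 h: 4 × 50 = 200 mg a day; 750 / 200 = 3.75 days.
- At the escalated 100 mg every 6 h: 4 × 100 = 400 mg, or 8 tablets, a day; 15 / 8 = 1.9 days.

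The 1.9 days assumes that the ERAS escalation continues at home on the discharge supply. On that assumption the tablets run out well before day 14, so refills or other opioids are foreseeable.

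**3. Oxycodone that a tramadol count cannot see**

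One dose of 5–10 mg every 4 h is at most 6 doses in 24 h: 6 × 5 = 30 mg to 6 × 10 = 60 mg. This is a per-patient ceiling. It cannot be turned into OME, because the protocol cites a conversion table without reproducing its factors. Nor can it be turned into an effect on the arm difference, because no escalation rate is given.

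**4. How far each data item reaches**

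| Place | Scope |
|---|---|
| Secondary Outcome measures, item 8 | any opiate converted to OME |
| Comparison, 24-hour call | tramadol pills used |
| Comparison, day 14, first item | tramadol pills left |
| Comparison, day 14, second item | tramadol pills left, set against refills |
| Comparison, 6 weeks | OME with no drug named; refills with the drug identified |
| Closing paragraph of Comparison | tramadol or narcotic prescription filled, and pills left |
| Analysis Plan/Statistics | all opioids in the electronic file are tallied |
| Outcomes table | tramadol pills, with room for other medications |

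The outcome definition covers every opioid. The items that collect OME at 24 hours and day 14 do not.

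**The case against.** The strongest defence is that the ERAS column is a set of hospital orders and the later list is the take-home prescription. The column includes intravenous ondansetron and intramuscular promethazine, and the list gives total tablet counts. On that view the description of tramadol as the only opiate concerns the prescription alone, and nothing conflicts. This is a reasonable reading, so a reader who infers that the two regimens are incompatible goes further than the documents allow. It does not close the matter: the split is never stated, the prescription text sends the reader to the ERAS table for its own details, and same-day discharge puts both lists inside the first day.

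Three further limits stand.

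- No passage leads to zero NSAIDs; the range is one or two. No passage expressly orders both lists to be given together.
- The sentence listing study medications, "0.25% bupivacaine, dexamethasone, acetaminophen, ibuprofen, QL blocks", names ibuprofen and not celecoxib, but it is weak support. It concerns FDA approval and coverage analysis, and it also omits tramadol and gabapentin.
- A reader might infer that all follow-up counts tramadol alone, or that every other opioid tablet taken at home scores zero. The 6-week items, the general narcotic question, the rule converting any opiate and the outcomes table all reach further. The gap lies in the 24-hour and day-14 items. The electronic-file tally does not plainly close it, since tablets taken at home are not obviously in that file.

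Finally, that surgeons would follow different lists is conjecture. Allocation is randomised and the surgeon is blinded to it, so such variation would mainly add noise.

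**Conclusion.** The point holds in limited form. The protocol contains an unreconciled inconsistency in a regimen that it calls the same for all patients: celecoxib against ibuprofen, and tramadol as the only opiate against a route to oxycodone or Nucynta. Depending on the reading, a patient could receive one or two NSAIDs.

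The 24-hour and day-14 OME items can also miss non-tramadol opioids taken at home, up to 30 to 60 mg of oxycodone per 24 hours in a patient on the full escalated schedule. This assumes that some escalated patients take those drugs after discharge and that the call follows the item as worded. A bias towards no difference needs the further assumption that escalation differs by arm; if it does not, the loss is mainly under-recording and noise.

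A reader might infer that the primary analysis is compromised. The documents do not support that. QoR-40 is not built from opioid counts; at most, uneven background analgesia adds some noise through its pain dimension. The point bears on safety and on the secondary OME outcome.

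**What to change.** 1. Reconcile the ERAS Post-Op column with the prescription text and list. State which applies in hospital, which applies at discharge, and how the two relate for a patient discharged the same day. Align the study-medication sentence with the result. Which drug or escalation rule is right is for the sponsor and clinicians; this review takes no position.
2. Reword the 24-hour and day-14 OME items to record every opioid taken since the last contact by name, strength and number of tablets.
3. State that these home counts are added to the in-hospital electronic record to form cumulative OME. The 6-week items are already not limited to tramadol; using the same format there would be for consistency only.

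The cost is protocol and case-report-form wording and slightly longer calls. Design, randomisation, sample size and the primary analysis do not change.

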During the telephone encounters or the clinical visits, patients will be asked if they filled their prescription for Tramadol/narcotic and how many pills they have left). If the patient is not seen at the 2 weeks mark for any reason, a telephone call will be done to collect that information by the surgeon.

6- Expected duration of study and subject participation.

We currently perform at the minimum 5 hysterectomies per week and Memorial Hermann Hospital (Laparoscopic and Robotic) and expect to randomize half of the patients, to complete the study within up to 2 years after IRB approval.

Sample Size and Power

- Based on previous studies, the mean standard deviation of QOR-40 after gynecologic laparoscopy are 150-170 and 10-15, respectively.
- A clinically significant difference would be 10-15.
- A sample size of 31 patients per group is needed to detect the difference of 20 points in the global QOR-40 score, a SD 25, with a Type 1 error of 5% and a power of 90%.
- 76 patients will be included to allow for a dropout rate of approximately 18%. Lost to follow up is expected to be low.

For pain scores in the VAS: Meaningful clinical difference in VAS scores is 30%

Analysis Plan/Statistics

- For baseline patient characteristics, continuous variables will be reported as medians with 25th and 75th percentiles (interquartile range [IQR]), and categorical variables as counts and percentages.
- To compare across groups, Kruskal-Wallis tests will be performed for continuous variables and Chi-square tests for categorical variables.
- CONSORT diagram will be performed
- Intention to treat analysis will be performed
- All unadjusted outcomes will be reported descriptively (mean SD/ median IQR)
- For all outcomes, we will conduct intent-to-treat Bayesian analysis to calculate probabilities of intervention benefits and harms. We will use neutral priors and exclude large treatment effects. We will report posterior medians of group differences, their corresponding 95% credible intervals, and probability of treatment benefit.

Primary outcome as QOR will be analyzed with a negative binomial regression model to account for expected skewness. The model will include group (local, QL), and type of surgery as covariates. We will account for surgery type (Robotic versus laparoscopic hysterectomy) simply because of the difference in port placement and port size between both approaches.

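### At the plan's own inputs, 31 per group is slightly too few for 90% power: two-sided formulas need 33 or 34, and 31 gives about 87–88%

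*Combined protocol and SAP*

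**What the plan says.** The Sample Size and Power section states: "A sample size of 31 patients per group is needed to detect the difference of 20 points in the global QOR-40 score", continuing with "a SD 25, with a Type 1 error of 5% and a power of 90" per cent. It then says "76 patients will be included to allow for a dropout rate of approximately 18" per cent, and adds "Lost to follow up is expected to be low".

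The section does not say which test lies behind the 31, or whether the 5% is one-sided or two-sided. Equal allocation is implied by a single per-group figure; Study Design and Procedures says only that patients are "block randomized to one of 2 arms: Local anesthesia and QL block".

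The Analysis Plan/Statistics section plans a negative binomial regression for the primary outcome, with group and type of surgery in the model, and a Bayesian analysis of all outcomes. No t-test is planned for QoR-40.

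**The concern.** A sample-size sentence that gives the difference, SD, error rate and power can be checked by anyone, and this one does not return its own answer under a standard two-means formula. The enrolment target is then built on it: 31 × 2 = 62, and 62 / 0.82 = 75.6, which rounds up to 76. If 31 is too low for 90% power, two statements in the plan are off. The stated power is a little high for 31 per group, and 76 patients cannot absorb an 18% loss and still hold 90%. The same sentence would probably be carried into the CONSORT-style report that the plan promises, where a reader could not reproduce it.

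**Working it through.** **Inputs, all from Sample Size and Power:** difference 20, SD 25, type 1 error 0.05, power 0.90, 31 per group, 76 enrolled, dropout about 18%. Standardised difference d = 20 / 25 = 0.80. **Assumptions:** equal allocation and an unadjusted comparison of two means. Sidedness is tried both ways.

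**1. The plan's dropout step reproduces.** 62 / (1 − 0.18) = 75.6, so 76. In reverse, 76 × 0.82 = 62.3, or about 31 per group.

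**2. Patients per group for 90% power.** Normal approximation: n = 2(z for α + z for power)² / d².
- Two-sided 5%: 2 × (1.960 + 1.282)² / 0.64 = 32.8, so 33.
- One-sided 5%: 2 × (1.645 + 1.282)² / 0.64 = 26.8, so 27.

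T-test (noncentral t, solved numerically):
- Two-sided 5%: 33.8, so 34.
- One-sided 5%: 27.5, so 28.

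None of these is 31. A rank test would not explain it either: assuming 0.955 efficiency relative to the t-test, the two-sided figure is 33.8 / 0.955 = 35.4, so 36.

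**3. Power at 31 per group.** Two-sided normal approximation: Φ(0.80 × √(31/2) − 1.960) = Φ(3.150 − 1.960) = Φ(1.190) = 88.3%. The other cases are in the table.

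| Evaluable per group | Two-sided, normal | Two-sided, t-test | One-sided, t-test |
|---|---|---|---|
| 31 (about 18% lost) | 88.3% | 87.3% | 92.9% |
| 33 | 90.1% | 89.3% | 94.2% |
| 34 | 91.0% | 90.2% | 94.7% |
| 36 (about 5% lost) | 92.4% | 91.7% | 95.7% |
| 38 (no loss) | 93.7% | 93.1% | 96.5% |

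**4. Dropout that 76 can absorb at two-sided 90% power.**
- T-test: 1 − 68/76 = 10.5%.
- Normal approximation: 1 − 66/76 = 13.2%.

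**5. What would make 31 correct.** With a two-sided t-test, 31 per group reaches 90% for a difference of 20.9 points at SD 25, or for an SD of 23.9 at 20 points. The latter is a variance reduction of 1 − (23.9/25)² = 8.6%. Under the normal formula the reduction needed is 1 − 31/32.84 = 5.6%.

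**The case against.** The strongest reply is that the gap is small and depends on choices the plan never made.

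- **Test.** The t-test is an assumption. With the two-sided normal formula the gap is 2 patients per group and 1.7 points of power, small enough to call the 31 approximate. This stands, which is why the result is given as a range. Both two-sided methods still err in the same direction.
- **Sidedness.** With a one-sided 5% test, 31 per group exceeds 90%, so power would not be overstated. That is true, but 31 would then not be the number needed, since 27 or 28 would do. Two-sided is the more natural reading: Analysis Plan/Statistics reports 95% intervals, and the main objective under General Information (PICO) asks which intervention is better without fixing a direction.
- **Model.** The primary analysis is a negative binomial regression adjusted for surgery type, so an unadjusted figure is not the power of the planned analysis. This stands. If surgery type explained about 6–9% of the variance, 31 would suffice on the two-means scale; the documents do not say how much it explains. However, the stated inputs are a mean difference and an SD, with no negative binomial parameters, so the planned model does not account for the 31.
- **Dropout.** A reader might infer that the design delivers only about 87% power. The documents do not support that as an unconditional statement. The primary outcome is collected by telephone at 24 hours, the plan expects little loss to follow-up, and power stays at 90% or above up to about 10–13% loss.

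**Conclusion.** The point holds as a modest arithmetic correction. At a 20-point difference, SD 25 and two-sided 5%, 90% power needs 33 or 34 evaluable patients per group, not 31; 31 gives 87.3–88.3%. No standard two-means calculation tried here, one-sided or two-sided, returns 31. The allowance of about 18% is correspondingly too generous: 76 enrolled holds 90% power up to about 10–13% loss.

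This rests on a two-sided, unadjusted comparison of two means with equal groups, which the plan implies but does not state. The shortfall is about 2 to 3 points and arises only near the full 18% loss; with no loss, t-test power is about 93%.

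A reader might also infer that the trial is underpowered and must enrol more. That does not follow, because on the plan's own expectation of low loss, 76 patients meet the 90% target at these inputs. Whether 20 points and SD 25 are the right inputs is a separate question, since the same section gives 10–15 for both the clinically significant difference and the SD in previous studies. This point takes the inputs as stated.

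**What to change.** Keep 76 patients. In Sample Size and Power, state that the 5% is two-sided (if that is the intention), and that the calculation is an unadjusted comparison of two means whereas the primary model is a negative binomial regression. Then replace the two figures with wording such as:

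*For a 20-point difference and SD 25, 33–34 evaluable patients per group (normal approximation or t-test, two-sided 5%) are needed for 90% power. Enrolling 76 allows about 10–13% dropout at 90% power; at 18% dropout (31 per group) power is about 87–88%.*

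If the investigators did use another method that gives 31, they should name it and give its inputs.

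The cost is a short rewording and a slightly less favourable stated figure. Enrolment, conduct and analysis do not change. Holding 90% power against a full 18% loss would instead take 66 / 0.82 = 80.5 or 68 / 0.82 = 82.9, that is 82 or 84 patients in equal groups. With loss expected to be low, that increase is not required.
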